7.1. Subject Disposition

Information regarding subject disposition will be summarized for all subjects. Summaries will include the number of the subjects who were screened, who failed the screen, who enrolled into the study, the subject number in each analysis population, the number of the subjects who completed the study and who discontinue the study early. For those who discontinue the study, the primary reason for discontinuation will be summarized.

7.2. Protocol Deviations

Protocol deviations will be collected throughout the duration of the study. Protocol deviations will be assigned a sponsor-defined category type, such as treatment compliance, study adherence, and use of prohibited therapies. Each deviation will be defined as important or minor. A tabular summary of the important deviations will be generated. In addition, a by-subject listing of all the protocol deviations will be produced.

7.3. Demographic and Baseline Characteristics

Demographics and baseline characteristic data will include age, sex, ethnicity, race, body weight (kg), height (cm), and baseline disease characteristics [BSA, BSA group ($\geq 5\%$ or $< 5\%$), IGA, I-IGA, PASI, and WI-NRS baseline scores]. Medical history will not be summarized in a table but will be displayed in a listing.

Continuous variables will be summarized using descriptive statistics. Categorical variables will be summarized using counts and percentages. Demographics and baseline characteristics will be summarized for the Safety population.

8. Efficacy Analysis

The Safety population will be used for efficacy analysis. Analyses using the Safety population will be based on treatment received.

8.1. Efficacy Variables

Efficacy will be an exploratory endpoint, with analyses including:

- Change and percent change from baseline in PASI score at each study visit
- Achievement of a 50% or greater and 75% or greater improvement in PASI score from baseline to each study visit
- Change and percent change from baseline in IGA score at each study visit
- Change and percent change from baseline in I-IGA score at each study visit
- Change and percent change from baseline in BSA involvement at each study visit
- Change and percent change from baseline in WI-NRS score at each study visit

8.2. Baseline Values

Unless otherwise noted, baseline is defined as the last non-missing value recorded prior to the first application of study drug. When applicable, unscheduled visits will be used in the determination of baseline values.

For subject local tolerability assessment, baseline is derived as the last non-missing measurement taken on Day 1 of first application of study drug. Baseline investigator local tolerability assessment is the last non-missing assessment prior to the first dose.

8.3. Handling of Dropouts or Missing Data

Subjects that withdraw or are discontinued from the study prior to Week 4 Visit, may be replaced. Unless described otherwise in subsequent sections, analyses will be carried out with the data available using no imputation for missing data. A description of how missing data will be handled for select endpoints is included below.

8.3.1. Coronavirus 19

Due to coronavirus disease 19 (COVID-19) outbreak during the course of the study, there may be several subjects who will have missing assessments which could affect the analysis. Subjects who are unable to attend a study visit due to COVID-19 will be documented in the protocol deviation log. The protocol deviation date will be used as the COVID-19 affected date (or visit). If a subject reports an adverse event of COVID-19,

then the event start date will be used as the affected date. In the event that a subject has an affected COVID-19 date from both sources, the earlier of the dates will be used.

Subjects who were affected by COVID-19 will be summarized in a data listing. The listing will contain the following information: subject number, treatment, gender, age, total study duration, exposure to study treatment, any COVID-19 related adverse events, completion/discontinuation of the study, and reasons for discontinuation.

8.4. Handling of repeat and unscheduled assessments

Unscheduled assessments are used when scheduled assessments are not collected. Unscheduled assessments will be assigned to the associated visit and timepoint based on date and time of assessment. If there are multiple unscheduled assessments assigned to the same visit, then the assessment closest to the scheduled visit will be used for analysis.

8.5. Interim Analysis and Data Monitoring

No interim efficacy analyses are planned. PK and safety data may be reviewed on an ongoing basis. Summaries may be generated for regulatory interaction.

8.6. Multiple Comparison/Multiplicity

No formal statistical comparisons are planned; thus, no adjustment for multiple comparisons is needed.

9. Methods of Efficacy Analysis

9.1. Psoriasis Area and Severity Index (PASI)

Psoriasis Area and Severity Index (PASI) assessment will be summarized at Baseline/Day 1, Week 2, and Week 4 visits. Assessments will be performed as single assessments from which PASIs will be calculated. PASI is used for the measurement of severity of psoriasis. PASI combines the assessment of the severity of lesions and the area affected into a single score in the range 0 (no disease) to 72 (maximal disease).

The body is divided into four sections (head (h) (10% of a person's); arms (a) (20%); trunk (t) (30%); legs (l) (40%)). Each of these areas is scored by itself, and then the four scores are combined into the final PASI/mPASI. For each section, the percent of area (A) of skin involved is estimated and then transformed into a grade from 0 to 6 (A):

0. 0% of involved area
1. < 10% of involved area
2. 10-29% of involved area
3. 30-49% of involved area
4. 50-69% of involved area

5. 70-89% of involved area
6. 90-100% of involved area

Within each area, the severity is estimated by four clinical signs: erythema ('E'; redness), induration ('T'; thickness), and desquamation ('S'; scaling). Severity parameters are measured on a scale of 0 to 4, from none to maximum severity possible.

To calculate the PASI, the sum of the severity rating for the three main signs are multiplied with the numerical value of the area affected and with the various percentages of the four body areas. These values are then added to complete the formula as follows:

$$\text{PASI} = 0.1 (\text{Eh} + \text{Th} + \text{Sh}) \text{Ah} + 0.2 (\text{Ea} + \text{Ta} + \text{Sa}) \text{Aa} + 0.3 (\text{Et} + \text{Tt} + \text{St}) \text{At} + 0.4 (\text{El} + \text{Tl} + \text{Sl}) \text{Al}$$

Descriptive statistics will be calculated for percent change from baseline and change from baseline in PASI score at each study visit. Improvement in PASI scores will be summarized at each study visit. For example, 75% improvement (PASI75) from baseline is when the percent change from baseline is 75% or greater and 50% or greater improvement (PASI50) from baseline is when percent change from baseline is at least 50%. Frequency counts and percentages will be compiled for PASI75 and PASI50 scores at each study visit.

9.2. Investigator Global Assessment (IGA) and Intertriginous Investigator Global Assessment (I-IGA)

Investigator Global Assessment (IGA) will be summarized at Baseline, Week 2, and Week 4. The IGA should be completed prior to other physician assessments. The IGA is a static evaluation of qualitative overall psoriasis severity. This global assessment scale is an ordinal scale with five severity grades (reported only in integers of 0 to 4). Each grade is defined by a distinct and clinically relevant morphologic description that minimizes inter-observer variability (see Table below). Descriptive statistics will be calculated for change and percent change from baseline in IGA score at each study visit. IGA success is defined as number of subjects who achieved IGA score of "clear" or "almost clear" plus ≥ 2 -grade improvement from baseline. The proportion of subjects who achieved IGA success will be summarized at each visit.

Score	Morphological Description
0 – Clear	Plaque thickening = no elevation or thickening over normal skin Scaling = no evidence of scaling Erythema = none (no residual red coloration but post-inflammatory hyperpigmentation may be present)
1 – Almost Clear	Plaque thickening = none or possible thickening but difficult to ascertain if there is a slight elevation above normal skin level Scaling = none or residual surface drying and scaling Erythema = light pink coloration

2 – Mild	Plaque thickening = slight but definite elevation Scaling = fine scales partially or mostly covering the lesions Erythema = light red coloration
3 – Moderate	Plaque thickening = moderate elevation with rounded or sloped edges Scaling = most lesions at least partially covered Erythema = definite red coloration
4 – Severe	Plaque thickening = marked or very marked elevation typically with hard or sharp edges Scaling = non-tenacious or thick tenacious scale, covering most or all of lesions Erythema = very bright red coloration; extreme red coloration; deep red coloration

For subjects with intertriginous area involvement of at least ‘mild’ severity by IGA (I-IGA ≥ 2) at Baseline (using the IGA scale shown above but evaluating intertriginous areas ONLY and NOT whole body involvement), an IGA for the intertriginous region alone (I-IGA) will be summarized at Baseline, Week 2, and Week 4. Descriptive statistics will be calculated for change and percent change from baseline in I-IGA score at each study visit along with I-IGA score at each visit.

9.3. Body Surface Area (BSA)

Body surface area assessments will be summarized at Baseline, Week 2, and Week 4. The BSA affected by plaque psoriasis will be determined by the subject’s hand method, where the subject’s hand (including fingers) surface area is assumed to equal 1% of body surface area (BSA). Descriptive statistics will be calculated for change and percent change from baseline at each study visit.

9.4. Worst Itch-Numerical Rating Scale (WI-NRS)

WI-NRS Assessments will be summarized at Baseline, Week 2, and Week 4. The WI-NRS has been developed as a simple, single item to assess the patient-reported severity of this symptom at its highest intensity during the previous 24-hour period. (Naegeli 2015). The WI-NRS will be determined by asking the subject’s assessment of worst itch over the past 24 hours. The scale is from ‘0 to 10’ (“no itch” to “worst imaginable itch”). WI-NRS pruritis assessment will be completed by subjects ≥ 8 years old, or by parent/caregiver for subjects < 8 years old. Descriptive statistics will be calculated for change and percent change from baseline in WI-NRS pruritus score at each study visit. WI-NRS success is defined as achievement of WI-NRS of 4-point reduction from baseline in subjects who had baseline WI-NRS $>= 4$. The WI-NRS success rate will be summarized at each visit.

9.5. Children’s Dermatology Life Quality Index (CDLQI)

The Children’s Dermatology Life Quality Index (CDLQI) (age 2-16) will be completed at Screening, Baseline, Week 2, and Week 4. CDLQI allows a simple, compact and uniform assessment of patients with skin diseases in general, in which higher scores indicate poorer disease-related quality of life. Subject/caregivers will complete the CDLQI. CDLQI will be displayed in a by-subject listing.

10. Safety Analysis

All safety analysis will be based on the Safety Population. Analysis using the Safety population will be based on the treatment received.

10.1. Exposure and Compliance

The number of IP applications by each subject based on diary data will be summarized using descriptive statistics appropriate for continuous variables. The amount of IP used by each subject based on tube weight will be summarized descriptively using continuous methods. The number of days on IP will be summarized descriptively.

A subject will be considered compliant with the dosing regimen if the subject applies at least 80% of the expected applications during the IP application period and does not miss more than 3 consecutive doses.

Investigational product application compliance will be calculated based on number of applications divided by the expected number of IP applications. Compliance will be summarized descriptively using the following categories: 100%, $\geq 80\%$ - $<100\%$, $< 80\%$.

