- d BSA, IGA affected by plaque psoriasis will be determined to qualify for study entry (Screening and Baseline) and will be measured at the Week 2 and Week 4 visits. Scalp, palms and soles should be excluded from consideration in these assessments. Additionally, Intertriginous Area-IGA (I-IGA), PASI, and WI-NRS will be evaluated. WI-NRS pruritus assessment will be completed by subjects  $\geq$  8 years old, or by parent/caregiver for subjects  $<$  8 years old. All other assessments will be performed by the Investigator or study staff, as appropriate.
- e Local tolerability assessments should be recorded prior to study drug application for the Investigator assessment of skin irritation (Berger and Bowman skin irritation score) and 10-15 minutes post-drug application for the subject's '0-3' burning/stinging assessment (subject-rating completed by the subject or parent/caregiver). At the Week 4 visit, only the Investigator assessment of skin irritation will be performed. Note for investigator tolerability assessments: reactions at the site of product IP application, which may occur post-Baseline, should be differentiated from the preexisting inflammation associated with the subject's psoriasis.
- f For females that have started menstruation, a serum pregnancy test will be performed during Screening. A urine pregnancy test will be administered to all females of child-bearing potential. A negative result is required for continued participation in the study, and results must be available prior to dispensing of study drug
- g All enrolled subjects will have a trough PK sample collected at the Week 4 visit. A subset of 6 subjects who consent will provide an additional PK sample pre-dose (within 1 hour) at the Week 2 visit.
- h Subjects/caregiver to apply assigned IP in clinic at Baseline and Week 2. All Investigator assessments should be completed prior to IP application.
- i The number of kits to be dispensed is based on %BSA affected. See IP Handling Manual for details. Site should review IP kit to ensure sufficient IP is available until the next visit and only dispense additional IP if needed.
- j Every tube should be weighed and recorded when dispensed and returned.
- k Any emergent AEs will be followed in the clinic for up to 1 month at the Investigator's discretion until resolved or otherwise judged as clinically stable.

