### 6.9.2 Treatment Administration

ARQ-151 cream 0.3% is administered once daily as a topical product to cover the skin surface at an application rate of approximately 2 mg/cm^2. Each site and each subject will be provided a digital scale to accurately measure the proper amount of cream to be applied to the psoriatic lesions. Each site will be provided a calculation program that uses the subject's height, weight, and %BSA of plaque psoriasis involvement to calculate the correct amount of ARQ-151 to be applied once a day to the psoriatic lesions.

At the Baseline visit, the **Investigator** will calculate daily IP to be applied in grams using the calculation tool.

- IP tubes will be weighed prior to and immediately after IP application (Cap On)
- IP will be weighed into a plastic dish using the digital scale

Investigator will confirm calculated IP adequately covers the entire involved area of plaque psoriasis. The Investigator can adjust IP usage up or down based on their clinical judgement or may consider the calculated expected IP weight as acceptable. The plastic dish should be reweighed after IP application to determine the actual amount of IP used.

At the Baseline visit, the study staff will demonstrate to the subject and/or parent/caregiver how to use the digital scale to measure the proper amount of ARQ-151 cream to apply. ARQ-151 cream is applied to psoriasis lesions as a thin film and rubbed in using the index and middle finger, thoroughly but gently, until the ‘white’ has disappeared. The subject or parent/caregiver will then apply the weighed amount of ARQ-151 to the psoriasis lesions once a day.

If a parent/guardian/caregiver helps apply the study medication, they should wash their hands with soap and water when finished.

For days that are a clinic visit, the IP will be applied in the clinic and the subject does not apply any further IP that day. All psoriasis lesions should be treated using the IP amount as noted in the Subject Body Diagram (see [Appendix 1](#)), except for the scalp.

Re-training will be conducted at subsequent visits as needed (i.e., if the returned tube(s) weighs substantially different than the expected weight).

Note:

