### **6.9.3 Treatment Compliance**

Investigational product tubes will be weighed at each clinic visit.

Subjects/caregivers will complete a daily diary recording the date and time of each dose applied, any missed doses, and a comment section should the subjects have a comment, e.g., record potential AEs. Site personnel will review the diaries and use the information to question the subject regarding compliance and AEs and then record appropriate information in source documents and complete Case Report Forms (CRFs). If a subject misses a dose, they should be instructed to return to the protocol investigational product administration schedule (i.e. if subject forgets a dose they should wait until that evening and apply as usual).

A subject will be considered compliant with the dosing regimen if the subject applies at least 80% of the expected applications during the study drug application period and does not miss more than 3 consecutive doses.

Compliance will be assessed by review of the dosing diary. Weight of investigational product applied (via dispensed and returned tube weights) will be measured for reporting purposes.

If the diary shows less than 80% of expected use, the subject is using too little study drug and retraining must be conducted and documented.

Compliance will be documented in source and in eCRF.

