### **8.1.7 Investigational Product Application Compliance**

The number of investigational product applications by each subject based on diary data will be summarized using descriptive statistics.

The amount of investigational product used by each subject based on tube weight will be summarized by treatment using descriptive statistics, and categorically.

Investigational product application compliance will be calculated based on number of applications divided by the expected number (amount) of investigational product applications for each subject. Compliance will be summarized descriptively by treatment group.

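### Compliance is a count of diary applications only, and no planned analysis compares the grams each child used with the grams calculated for that child

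*SAP*

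**What the plan says.** **Compliance measure.** SAP 10.1: "Investigational product application compliance will be calculated based on number of applications divided by the expected number of IP applications". Protocol 6.9.3 names the source: "Compliance will be assessed by review of the dosing diary". It says tube weights are taken for reporting. The diary contents listed there are the date and time of each dose, missed doses and comments; grams are not listed.

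**Compliant child.** Under SAP 10.1 this is a child who "applies at least 80% of the expected applications during the IP application period and does not miss more than 3 consecutive doses". The ratio is tabulated in three bands: exactly 100%, 80% to below 100%, and below 80%. The SAP does not define the expected number.

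**Grams.** SAP 10.1 also summarises the amount used by tube weight as a continuous variable, with the number of applications and days on treatment. Protocol 8.1.7 plans a categorical summary of the amount as well, and words the compliance ratio as "number of applications divided by the expected number (amount) of investigational product applications for each subject". The SAP carries over neither the categorical summary nor the word in parentheses.

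**Intended amount.** Protocol 6.9.2 gives each site a tool that uses height, weight and percent body surface area to "calculate the correct amount of ARQ-151 to be applied once a day to the psoriatic lesions", at about 2 mg/cm². The Investigator confirms or adjusts the result, and each subject receives a digital scale. Tubes are weighed when dispensed and returned (Protocol Section 2, footnote j).

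**Clinic doses.** Protocol Section 2, footnote h: "Subjects/caregiver to apply assigned IP in clinic at Baseline and Week 2". Protocol 6.9.2: "For days that are a clinic visit, the IP will be applied in the clinic".

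**The concern.** In a maximal-usage study the key question about adherence is whether the intended amount reached the skin. A diary count answers a different one: whether something was applied each day. Protocol 6.9.3 blurs the two, because it treats a diary below 80% of expected use as a sign that too little drug is being used.

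The separate gram summary does not close the gap. Expected grams differ from child to child, since entry requires at least 2% involvement with no upper limit, and SAP 7.3 groups children on both sides of 5%. A pooled mean and SD of grams cannot tell a child with little disease who used everything from a child with more disease who used half.

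The first primary objective is systemic exposure, which the synopsis places under maximal usage conditions. If a child in the subset under-applies, plasma levels will be lower for a reason the compliance table cannot show.

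**Working it through.** The plan states no compliance figure, so there is nothing to reproduce.

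**1. Diary ratio against gram ratio**

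Inputs: once-daily application for 28 days (SAP Section 3); about 2 mg/cm² (Protocol 6.9.2); 3% involvement, the minimum for the maximal-usage subset. Total body surface is not given, so I assume 1.0 m² with a range of 0.8 to 1.4 m².

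- Daily grams = body surface (cm²) × fraction involved × 2 mg/cm². At 1.0 m²: 10,000 × 0.03 × 2 = 600 mg = 0.6 g (range 0.48 to 0.84 g).
- Expected over 28 applications: 0.6 × 28 = 16.8 g (13.4 to 23.5 g).
- A child using half each time uses 8.4 g (6.7 to 11.8 g).
- Diary compliance = 28/28 = **100%**, the top band.
- Gram compliance = 8.4/16.8 = **50%**.

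The body-surface assumption changes the grams but not the 50%, because it cancels in the ratio.

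**2. Why absolute grams do not reveal this**

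At 1.0 m² and 6% involvement, expected use is 10,000 × 0.06 × 2 = 1.2 g a day, or 1.2 × 28 = 33.6 g. A recorded 16.8 g is then full use at 3% (16.8/16.8 = 100%) and half use at 6% (16.8/33.6 = 50%). The same tube weight has opposite meanings.

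**3. Weight of one child**

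The subset is 6 evaluable children, so one under-user is 1/6 = 16.7% of it.

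**4. The undefined denominator**

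The Week 4 window is Day 28 ± 3, and Protocol Appendix 6 allows up to 14 further days of dosing (Day 42). For a child who misses nothing and whose last dose is the day before the visit:

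| Week 4 visit | Applications | If expected is fixed at 28 | If expected is own dosing period |
|---|---|---|---|
| Day 25 | 24 | 85.7% | 100% |
| Day 28 | 27 | 96.4% | 100% |
| Day 29 | 28 | 100% | 100% |
| Day 31 | 30 | 107.1% (no band) | 100% |
| Day 42 | 41 | 146.4% (no band) | 100% |

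The misfit with the bands appears only in the fixed-28 column. Values above 100% under the other reading need extra applications.

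**5. Week 4 dose**

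The schedule and footnote h show in-clinic application at Baseline and Week 2 only, which gives 27 applications to Day 28. The 28-day wording and the clinic-day rule in Protocol 6.9.2 point to 28. The difference is one dose, 1/28 = 3.6 percentage points.

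**The case against.** The strongest reply is that the plan separates adherence from exposure on purpose. Protocol 6.9.3 and SAP 10.1 agree that compliance comes from the diary, and grams are reported alongside it. Protocol 6.9.2 compares actual with expected use and calls for retraining when they differ substantially. With about 20 children and by-subject listings (SAP Section 5), a reader could inspect grams case by case. Compliance defines no analysis population, and no inference is planned. PK detail is left to a separate report, which may relate amount to concentration.

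Most of this stands. A reader might infer that the plan ignores grams; it does not. What is missing is grams relative to the child's own target. The retraining rule gives no threshold and is not an analysis, and neither document commits the PK report to this comparison.

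Three other stronger readings also fail:

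- **That the bands contradict the schedule.** This needs a denominator of 28, which neither document states for compliance. The reference to the application period in SAP 10.1 and to each subject in Protocol 8.1.7 favour an individual denominator.
- **That the SAP removed a weight-based measure.** In Protocol 8.1.7 the numerator is a count of applications, and dividing a count by an amount makes no sense. Dropping the word may simply have removed an ambiguity.
- **That exposure results would be uninterpretable.** Grams used are still reported, so interpretation is weakened, not lost.

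**Conclusion.** The point holds as a gap in a descriptive analysis. No planned analysis in these documents shows whether each child applied the calculated amount, and a child at half the amount can be classed as 100% compliant. That 50% against 100% contrast rests only on every application being recorded; the gram figures also rest on the assumed body surface.

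The practical consequence is largest in the subset of 6, where under-application could be mistaken for low absorption. The documents give no evidence of how often under-application will occur, so the effect on measured exposure cannot be sized.

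The undefined denominator and the absence of a band above 100% are secondary matters of missing detail. Separately, the clinic-day text and the schedule disagree on whether cream is applied at the Week 4 visit, and the sponsor must reconcile them.

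**What to change.** In SAP 10.1:

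1. Keep the diary measure and add, for each child, grams used by tube weight ÷ (calculated, Investigator-confirmed daily grams × expected applications in that child's own dosing period). Summarise it for all children. For the maximal-usage subset, list it beside each concentration; tubes are weighed at Week 2 and Week 4, so it can be calculated up to the sampling visit.
2. Define expected applications as each child's own dosing period, including any COVID-19 extension days and excluding interruptions directed under Protocol 7.9. Whether the Week 4 visit day counts should follow from the sponsor's reconciliation of Protocol 6.9.2 with the schedule and footnote h.
3. Change the top band to 100% or more.

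The cost is a few lines of SAP text and one derived variable, from tube weights and daily amounts the study already produces. The ratio is approximate: tube weight includes waste, and because new lesions are treated while the daily amount is calculated at Baseline, a child using the cream correctly can exceed 100%. It should be read as a guide to large departures, with no pass mark attached.
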